2. INTRODUCTION

This document describes the rules and conventions to be used in the presentation and analysis of efficacy and safety data for Protocol TED-C14-006. It describes the data to be summarized and analyzed, including specifics of the statistical analyses to be performed. Pharmacokinetic (PK) concentration will be summarized but the analysis of PK parameters will be detailed in a separate analysis plan.

This statistical analysis plan (SAP) is based on protocol amendment 4, dated 15 March 2016.

3. STUDY OBJECTIVES

The objective of this clinical study is to evaluate the safety, pharmacokinetics, and efficacy/pharmacodynamics (PD) of teduglutide in pediatric subjects through 17 years of age with short bowel syndrome (SBS) and who are dependent on parenteral support.

4. STUDY DESIGN

4.1. GENERAL DESCRIPTION

This study will include 2 treatment arms: a teduglutide treatment arm and a standard of care treatment arm. Subjects in both arms will participate in a 2-week minimum screening period, a 24-week treatment period, and a 4-week follow-up period. During the screening period, subjects will choose into which arm to enroll. During the 24-week treatment period, subjects in the standard of care treatment arm will receive standard medical therapy of SBS, while those in the teduglutide treatment arm will receive daily subcutaneous injections of teduglutide (study drug) in addition to standard medical therapy. The teduglutide treatment arm subjects will be randomized 1:1 in a double-blinded manner into two parallel teduglutide dose groups: 0.025 mg/kg/day and 0.05 mg/kg/day. Randomization across dose groups will be stratified by age: <1 year, 1 to <12 years, 12 to <17 years, and 17 to <18 years.

All subjects will be screened for a minimum of 2 weeks prior to start of treatment to verify the requirements for nutritional support for each subject and to ensure adherence to eligibility parameters. After screening, the 24-week treatment period will consist of site visits at baseline, weekly for the first 2 weeks (week 1 and 2), and then every other week through week 12 (week 4, 6, 8, 10, and 12). For the remainder of the treatment period, visits at the sites will be conducted every 3 weeks (at week 15, 18, 21, and 24). Telephone contacts will be made on all other weeks during the treatment period. The subjects in both arms will follow the same visit schedule. At all site visits and telephone contacts, safety will be monitored and nutritional

Document:	\\quintiles.net\Enterprise\Apps\sasdata\SASa\sas\Shire\Teduglutide\Biostatistics\Documentation\SAP\TE D-C14-006_SAP_Final_V1.0_20170714		
Author:	PPD	Version Number:	Final V1.0
		Version Date:	14Jul2017
Template No:	CS_TP_BS016 – Revision 3	Reference:	CS_WI_BS005
Effective Date:	01May2012		

support will be reviewed and adjusted as needed. At the end of the treatment period (week 24/EOT), all subjects will enter a 4-week follow-up period until the end of study (week 28/EOS) during which time no study drug (ie, teduglutide) will be administered. A final visit will be scheduled at week 28, 4 weeks following week 24 or the end of treatment (EOT). Telephone contact will be made during the interim weeks from EOT to end of study (EOS) to monitor safety and any changes in nutritional support.

To maintain consistency across all centers, sites and subjects (randomized and standard of care) should be made to follow the nutritional support adjustment guidelines (developed with SBS expert input and provided in the protocol) for decisions regarding parenteral nutrition/intravenous fluid (PN/IV) support reduction and advances in enteral feeds based on weight gain, urine and stool output, and clinical stability.

Document:	\\quintiles.net\Enterprise\Apps\sasdata\SASa\sas\Shire\Teduglutide\Biostatistics\Documentation\SAP\TE D-C14-006_SAP_Final_V1.0_20170714		
Author:	PPD	Version Number:	Final V1.0
		Version Date:	14Jul2017

[figure not shown]
Template No: CS_TP_BS016 – Revision 3
Effective Date: 01May2012

Reference: CS_WI_BS005

Copyright © 2012 Quintiles Transnational Corp. All rights reserved.

The contents of this document are confidential and proprietary to Quintiles Transnational Corp. Unauthorized use, disclosure or reproduction is strictly prohibited.

Table A Study Diagram

4.2. SCHEDULE OF EVENTS

Schedule of events can be found in Section 6 (Table 6-2, Table 6-3, Table 6-4, and Table 6-5) of the protocol.

4.3. CHANGES TO ANALYSIS FROM PROTOCOL

There is no change of analysis from protocol. The protocol defines the efficacy population as all enrolled subjects. The analysis plan refers to the efficacy population as the Intention-to-Treat (ITT) population, which is the same as the efficacy population.

Document: \\quintiles.net\Enterprise\Apps\sasdata\SASa\sas\Shire\Teduglutide\Biostatistics\Documentation\SAP\TE D-C14-006_SAP_Final_V1.0_20170714

Author: PPD Version Number: Final V1.0
Version Date: 14Jul2017

Template No: CS_TP_BS016 – Revision 3
Effective Date: 01May2012

Reference: CS_WI_BS005

Copyright © 2012 Quintiles Transnational Corp. All rights reserved.

The contents of this document are confidential and proprietary to Quintiles Transnational Corp. Unauthorized use, disclosure or reproduction is strictly prohibited.

5. PLANNED ANALYSES

The following analyses will be performed for this study:

- Final Analysis

5.1. FINAL ANALYSIS

All final, planned analyses identified in this SAP will be performed by Quintiles biostatistics following sponsor authorization of this statistical analysis plan, database lock, sponsor authorization of analysis sets and unblinding of treatment.

Pharmacokinetic concentration data will be summarized but the analyses of PK parameters will be performed by a Shire designated vendor in accordance with the PK SAP.

6. ANALYSIS SETS

Analysis of efficacy and safety endpoints will be performed based on the analysis sets defined in this section and as specified for each endpoint throughout this SAP. Inclusion/exclusion of subjects from each analysis set will be confirmed prior to the unblinding of the study based on blinded data review.

6.1. ALL SUBJECTS SCREENED [SRN] SET

The all subjects screened (SRN) set will contain all subjects who provide signed informed consent for the study.

Data for subjects who fail to pass the screening period will be included in the listings but will not be included in any analyses.

6.2. ALL SUBJECTS ENROLLED [ENR] SET

The all subjects enrolled (ENR) set will contain all subjects who provide informed consent for this study, satisfy all of the inclusion criteria and none of the exclusion criteria defined in the protocol and make the choice of treatment arm (ie. teduglutide or standard of care) at the baseline visit.

Document:	\\quintiles.net\Enterprise\Apps\sasdata\SASa\sas\Shire\Teduglutide\Biostatistics\Documentation\SAP\TE D-C14-006_SAP_Final_V1.0_20170714		
Author:	PPD	Version Number:	Final V1.0
		Version Date:	14Jul2017

Template No: CS_TP_BS016 – Revision 3
Effective Date: 01May2012

Reference: CS_WI_BS005

Copyright © 2012 Quintiles Transnational Corp. All rights reserved.

The contents of this document are confidential and proprietary to Quintiles Transnational Corp. Unauthorized use, disclosure or reproduction is strictly prohibited.

6.3. INTENTION-TO-TREAT [ITT] SET

The intention-to-treat (ITT) set will contain all subjects in the ENR set; subjects will be classified according to treatment arm (teduglutide or standard of care), and within the teduglutide treatment arm, according to dose group (0.025 or 0.05 mg/kg).

All efficacy analyses will be conducted on this population, unless otherwise specified.

6.4. PER PROTOCOL [PP] SET

The per protocol (PP) set will contain all subjects in the ITT who complete the study treatment period without protocol deviations or other situations that could potentially affect the efficacy conclusions of the study.

The situations that may affect inclusion in the PP set include:

- Uninterpretable PK data
- Non-compliance to study drug for the treatment group as defined in Section 15
- Clinically significant discrepancies between planned and actual treatment
- Missing baseline or week 24 efficacy data

6.5. SAFETY [SAF] ANALYSIS SET

The safety analysis set will contain all subjects who meet the following criteria:

- Teduglutide treatment arm: subjects who receive at least 1 dose of teduglutide and have undergone at least 1 post-baseline safety assessment; analyses will be performed according to dose group as appropriate.
- Standard of care treatment arm: subjects who have undergone at least 1 post-baseline safety assessment

Subjects will be classified according to treatment arm and the teduglutide dose they actually received. All safety analyses will be conducted on this population, unless otherwise specified.

6.6. PHARMACOKINETIC [PK] SET

The pharmacokinetic set will contain all enrolled subjects who receive at least one subcutaneous injection of teduglutide and have evaluable and interpretable PK data. Subjects

Document:	\\quintiles.net\Enterprise\Apps\sasdata\SASa\sas\Shire\Teduglutide\Biostatistics\Documentation\SAP\TE D-C14-006_SAP_Final_V1.0_20170714		
Author:	PPD	Version Number:	Final V1.0
		Version Date:	14Jul2017

Template No: CS_TP_BS016 – Revision 3
Effective Date: 01May2012

Reference: CS_WI_BS005

Copyright © 2012 Quintiles Transnational Corp. All rights reserved.

The contents of this document are confidential and proprietary to Quintiles Transnational Corp. Unauthorized use, disclosure or reproduction is strictly prohibited.

will be classified according to dose group (0.025 or 0.05 mg/kg) in the teduglutide treatment arm.

7. GENERAL CONSIDERATIONS

7.1. REFERENCE START DATE AND STUDY DAY

Study Day will be calculated from the reference start date, and will be used to show start/stop day of assessments and events.

Reference start date for teduglutide arms is defined as the day of the first dose of study drug (Day 1), while for standard of care treatment arm it is defined as the day of the baseline visit date. Study days before the first dose of study drug (or baseline) will be negative.

If the date of the event is on or after the reference start date then:

$$\text{Study Day} = (\text{date of event} - \text{reference start date}) + 1.$$

If the date of the event is prior to the reference start date then:

$$\text{Study Day} = (\text{date of event} - \text{reference start date}).$$

In the situation where the event date is partial or missing, the date will appear partial or missing in the listings, and Study Day, and any corresponding durations will be presented based on the imputations specified in [Appendix 2](#), Partial Date Conventions.

7.2. BASELINE

Unless otherwise specified, baseline is defined as the last non-missing measurement taken prior to or on the reference start date (including unscheduled assessments). For adverse events (AE) or concomitant medications that start on the reference start date, the time of onset will be compared to the time of the first dose of study drug to determine if the AE or medication was pre-baseline or post-baseline. If the timing relative to the first dose of study drug is unknown, AEs and medications commencing on the reference start date will be considered post-baseline. Actual PN/IV and EN administration on the day of the reference start will be considered post-baseline.

7.3. RETESTS, UNSCHEDULED VISITS AND EARLY TERMINATION DATA

In general, for by-visit summaries, data recorded at the nominal visit will be presented. Unscheduled measurements will not be included in by-visit summaries, but can contribute to

Document:	\\quintiles.net\Enterprise\Apps\sasdata\SASa\sas\Shire\Teduglutide\Biostatistics\Documentation\SAP\TE D-C14-006_SAP_Final_V1.0_20170714		
Author:	PPD	Version Number:	Final V1.0
		Version Date:	14Jul2017

Template No: CS_TP_BS016 – Revision 3
Effective Date: 01May2012

Reference: CS_WI_BS005

Copyright © 2012 Quintiles Transnational Corp. All rights reserved.

The contents of this document are confidential and proprietary to Quintiles Transnational Corp. Unauthorized use, disclosure or reproduction is strictly prohibited.

the EOS/EOT value, or best/worst case value where applicable. Unscheduled PN/IV or EN prescription adjustments carry forward until the net adjustment, and as such, may contribute to data assigned to subsequent visits.

Listings will include scheduled, unscheduled, retest and early discontinuation data.

7.4. WINDOWING CONVENTIONS

Nominal visits will occur within two days of the scheduled week 1 and week 2 visits, within three days of the scheduled week 3 to week 27 visits and within four days of the week 28 (EOS) visit. There will be no windowing of scheduled visits based on study day, and unscheduled visits will not be included in by-visit summaries. Early termination data will be mapped to a scheduled visit if it falls into the appropriate visit window as defined in the protocol and if that scheduled visit did not occur.

An End of Treatment (EOT) time point, defined as the last determination of endpoint or last available measurement after the date of first dose during the 24-week treatment period, will be analyzed in addition to the scheduled visits.

7.5. STATISTICAL TESTS

Due to the limited size of the study population descriptive statistics will be used with a goal of summarizing the sample. As such, no claims of significance will be made for any of the data.

Continuous variables, including those assessed on a discrete scale, will be summarized using descriptive statistics including number of subjects, mean, median, standard deviation, maximum, and minimum. For categorical variables, statistical summaries will include number of subjects and percentages.

7.6. COMMON CALCULATIONS

For quantitative measurements, change from baseline will be calculated as:

Test Value at Visit X – Baseline Value

Percent change from baseline will be calculated as:

$$\frac{((\text{Test Value at Visit X} - \text{Baseline Value}) / \text{Baseline Value}) * 100}{}$$

Change (or percent change) from baseline tables will be calculated based on the number of subjects in the treatment group with a non-missing value at baseline and at the time point being analyzed.

Document:	\\quintiles.net\Enterprise\Apps\sasdata\SASa\sas\Shire\Teduglutide\Biostatistics\Documentation\SAP\TE D-C14-006_SAP_Final_V1.0_20170714		
Author:	PPD	Version Number:	Final V1.0
		Version Date:	14Jul2017
Template No:	CS_TP_BS016 – Revision 3	Reference:	CS_WI_BS005
Effective Date:	01May2012		

7.7. SOFTWARE VERSION

All analyses will be conducted using SAS version 9.4 or higher.

8. STATISTICAL CONSIDERATIONS

8.1. ADJUSTMENTS FOR COVARIATES AND FACTORS TO BE INCLUDED IN ANALYSES

No adjustments for covariates are planned for the statistical analyses.

8.2. MULTICENTER STUDIES

This study will be conducted by multiple investigators at multiple centers internationally. Randomization to treatment arms is not stratified by country/ center.

8.3. MISSING DATA

Missing data will in general not be imputed. However, partial dates will contribute to analyses as described in [Appendix 2](#). All available data will be included in the safety analysis.

Details for the imputation algorithm for the missing endpoint values for PN/IV support parameters (volume, calories and etc.) will be described in Section [17.1.1](#) of this analysis plan.

8.4. MULTIPLE COMPARISONS/ MULTIPLICITY

Given the small sample size, no hypothesis testing will be conducted. Therefore, there will be no adjustment for alpha level.

8.5. EXAMINATION OF SUBGROUPS

Subgroup analyses will be conducted as stated in the exploratory analysis section. The following subgroups will be assessed and described within the section:

- Age group (years) at screening
 - o <1
 - o 1 to <12

Document: \\quintiles.net\Enterprise\Apps\sasdata\SASa\sas\Shire\Teduglutide\Biostatistics\Documentation\SAP\TE
D-C14-006_SAP_Final_V1.0_20170714

Author: **PPD** Version Number: Final V1.0
Version Date: 14Jul2017

Template No: CS_TP_BS016 – Revision 3
Effective Date: 01May2012

Reference: CS_WI_BS005

Copyright © 2012 Quintiles Transnational Corp. All rights reserved.

The contents of this document are confidential and proprietary to Quintiles Transnational Corp. Unauthorized use, disclosure or reproduction is strictly prohibited.

- o 12 to <17
- o 17 to <18
- Enteral glutamine use (Yes/No) at least once during the 24-week treatment period

9. OUTPUT PRESENTATIONS

[Appendix 1](#) shows conventions for presentation of data in outputs. The output templates provided together with this SAP describe the presentations for the analyses of this study based on Shire internal standards TFLs4ShireFinalV6.0. The format and content of the summary tables, figures and listings (TFLs) will be provided by Quintiles Biostatistics.

10. DISPOSITION AND WITHDRAWALS

All subjects who provide informed consent will be accounted for in this study.

Assessment of eligibility to the inclusion and exclusion criteria will be performed at Screening and re-confirmed at the Baseline visit.

Protocol deviations (as defined in Section 6.4) as obtained from a clinical trial management system (CTMS) will be assessed throughout the study. All identified deviations will be reported in the CTMS. Protocol deviations from the CTMS will be coded to categories and provided as part of the CTMS transfer to Biostatistics.

Subjects who discontinue the study prior to completion (through week 28 or EOS) will have their reason for discontinuation documented in the eCRF. Regardless of the reason for early discontinuation, all data available for the subject at the time of completion/discontinuation will be recorded on the eCRF and included in the analyses.

The presentation of planned listings will include the following:

- Subject Disposition (SRN set)
- Inclusion and exclusion criteria violations (SRN set)
- Protocol deviations (ENR set).
- Subjects excluded from Per Protocol Set (ENR set)
- Assignment to analysis sets (ENR set)

The following summary tables are planned for presentation:

- Subject disposition (SRN set) by region and overall

Document:	\\quintiles.net\Enterprise\Apps\sasdata\SASa\sas\Shire\Teduglutide\Biostatistics\Documentation\SAP\TE D-C14-006_SAP_Final_V1.0_20170714		
Author:	PPD	Version Number:	Final V1.0
		Version Date:	14Jul2017
Template No:	CS_TP_BS016 – Revision 3	Reference:	CS_WI_BS005
Effective Date:	01May2012		

- Analysis sets (ENR set)
- Summary of site visits (ENR set)
- Major protocol deviations (ENR set)

11. DEMOGRAPHIC AND OTHER BASELINE CHARACTERISTICS

Demographic data and other baseline characteristics will be presented for the ITT and PP Analysis Sets.

The following demographic and other baseline characteristics will be summarized for this study:

- Age (years) - calculated as a continuous parameter relative to date of screening. If partial date of birth date is entered with missing day and/or month due to regulatory constraints, age information will be obtained from Interactive Voice Response System (IVRS); if it is not available in IVRS, birth date will be imputed as the first day of the month if day is missing or first day of the year if both day and month are missing.
- Age Group – Age is categorized in pre-defined groups: <1, 1 to <12, 12 to <17, 17 to <18
- Sex (with reproductive status for females)
- Race
- Ethnicity
- Height Z-score at Baseline
- Weight Z-score at Baseline
- Head Circumference Z-score at Baseline (only for subjects who are \leq 36 months of age)
- BMI Z-score at Baseline

The demographic data collected in the eCRF will be listed by subject for the ENR set.

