4.2 Inclusion Criteria

Male and female children and adolescents, through 17 years of age, who meet the following inclusion criteria will be enrolled in the study.

1. Informed consent by a parent or guardian or emancipated minor prior to any study-related procedures
2. When applicable, an informed assent by the subject (as deemed appropriate by the Ethics Committee/Institutional Review Board) prior to any study-related procedures
3. Current history of SBS as a result of major intestinal resection, (eg, due to necrotizing enterocolitis, midgut volvulus, intestinal atresia, or gastroschisis)
4. Short bowel syndrome that requires PN/IV support that provides at least 30% of caloric and/or fluid/electrolyte needs prior to screening
5. Stable PN/IV support, defined as inability to significantly reduce PN/IV support, usually associated with minimal or no advance in enteral feeds (ie, 10% or less change in PN or advance in feeds) for at least 3 months prior to and during screening, as assessed by the investigator. Transient instability for events such as interruption of central access or treatment for sepsis is allowed if the PN/IV support returns to within 10% of baseline prior to the event.

6. Sexually active female subjects of child-bearing potential (in the active treatment group only) must use medically acceptable methods of birth control during and for 4 weeks after the treatment period

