9.3 Subject Data Protection

All data provided to the sponsor/designee will be identified only by subject number and initials, thereby ensuring that the subject's identity remains unknown. Where allowed, the subject's date of birth will also be recorded. The subject and/or the subjects' parent or guardian should be informed in writing, that the subject's data will be stored and analyzed in a

computer, with confidentiality maintained in accordance with national and local legislation. Study site-specific information must be added to the consent/assent as appropriate.

The subjects and/or the subjects' parent or guardian also should be informed in writing that authorized representatives of the sponsor/designee and/or regulatory authorities may require access to those parts of the hospital/clinic records which are relevant to the study, including medical history, for data verification purposes.

The principal investigator is responsible for keeping a subject identification list of all subjects screened and enrolled which includes the following information: subject number, full name, and a secondary unique identifier (ie, hospital/clinic number). A list of subjects who failed screening must also be maintained and be available for inspection.

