19.6.1. VITAL SIGNS SPECIFIC DERIVATIONS

- BMI

$BMI = 10000 * \text{Body weight (kg)} / \text{body height (cm)}^2$, where both body weight and body height data are available at the same scheduled visit

- Height, Weight, Head Circumference and BMI Z-scores

Official and validated SAS programs created by Centers for Disease Control and Prevention (CDC) will be used to calculate the Z-scores (standard deviations) for a child's sex and age (up to 20 years of age) for BMI, weight, height, and head circumference based on the CDC growth charts for children age 2 years and older and the WHO growth charts for infants and children < 2 years of age. For more information on the CDC SAS programs, see http://www.cdc.gov/growthcharts/computer_programs.htm.

Z-scores are calculated as the formula below:

$$Z\text{-score} = [((\text{observed value} / M) ^ L) - 1] / (S * L)$$

In which 'observed value' is the child's height, weight, head circumference or derived BMI. The L, M, and S values vary according to the child's sex and age. For more information on the LMS method, see <http://www.ncbi.nlm.nih.gov/pmc/articles/PMC27365/>.

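### If IVRS holds no age, a birth date known only to the year becomes 1 January, overstating age by about 6 months on average and lowering height, weight and head-circumference Z-scores in growing children

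*SAP*

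**What the plan says.** SAP section 11 defines age as "calculated as a continuous parameter relative to date of screening". For a birth date left partial by regulatory constraints, it sets a sequence. First, "age information will be obtained from Interactive Voice Response System (IVRS); if it is not available in IVRS", then "birth date will be imputed as the first day of the month if day is missing or first day of the year" (the last option when day and month are both missing). The protocol, in section 9.3, makes incomplete dates foreseeable: "Where allowed, the subject's date of birth will also be recorded".

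Two later outputs use this age:

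- **Age bands.** "Age is categorized in pre-defined groups: <1, 1 to <12, 12 to <17, 17 to <18" (SAP section 11). There is no band from 18 upwards and no rule for an imputed age that lands there. The bands serve the age subgroups (SAP 8.5 and 17.2.1.1) and the vital-sign tables (SAP 19.6).
- **Growth Z-scores.** SAP 19.6.1 uses the LMS formula and notes: "The L, M, and S values vary according to the child's sex and age". It does not say which age or birth date enters the program when the recorded date is partial. Z-scores are reported at baseline (SAP 11) and, as levels, changes and box plots, at site visits (SAP 19.6).

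**The concern.** An imputed date at the start of the period is the earliest date the child could have been born, so the error has only one sign. It does not average out across children, as it would with a date in the middle of the period.

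The Z-score compares the child with a reference for an older child. Where the reference median rises with age, the child looks smaller for age than is true. Arms are small (at least 10 per dose group, up to 8 in standard of care), so one misdated young child can visibly shift a mean or stand out in a box plot. The same error can move a child across an age-band limit, the switch of growth chart at 2 years or the 36-month limit for head circumference. At the top end, it can leave a child in no band at all.

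**Working it through.** The documents state no figure on this point, so there is none to reproduce. Growth rates, SDs, the value of S and the spread of dates below are assumptions.

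**1. Error in age.** Error = true birth date minus imputed birth date.

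- Year only known: 0, 1, ..., 364 days. Mean = (0 + 364)/2 = 182 days, or 0.50 year. It is zero only for a birth on 1 January.
- Day missing: day of month minus 1, so 0 to 30 days. The mean over the 365 birth days is 14.7 days. It is zero for births on the 1st.

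The error is never negative.

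**2. Direction of the Z-score.** The SAP formula is Z = [(X/M)^L − 1]/(S × L). At fixed L and S, its derivative with respect to M is −(X/M)^L/(S × M), which is negative for every L. As a check, take X = M, assume S = 0.045 and raise M by 2%. Z moves from 0 to between −0.43 and −0.45 for L from −2 to 2. The median rises with age for height, weight and head circumference while a child grows. The documents do not show whether the BMI median rises or falls at a given age, so no direction can be assigned to BMI Z.

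**3. Size for height, year only known.** Shift ≈ −(error in years × growth per year)/SD.

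| Assumed growth, SD | Mean error 0.5 year | Maximum, about 1 year |
|---|---|---|
| 6 cm/year, 5 cm | 0.5 × 6/5 = 0.6 low | 1.2 low |
| 9 cm/year, 3.5 cm | 0.5 × 9/3.5 = 1.3 low | 2.6 low |
| 12 cm/year, 3 cm (fast early growth) | 0.5 × 12/3 = 2.0 low | 4.0 low |
| 5 cm/year, 7 cm | 0.5 × 5/7 = 0.36 low | 0.71 low |
| 0.5 cm/year, 7 cm (near adult height) | 0.5 × 0.5/7 = 0.04 low | 0.07 low |

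With the day alone missing, 14.7/365 = 0.040 year. The first two rows then give 0.040 × 6/5 = 0.05 and 0.040 × 9/3.5 = 0.10. In an arm of 10, one year-only child with a shift of 0.6 to 1.3 moves the mean height Z by 0.06 to 0.13.

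**4. Change from baseline.** The same age error applies at every visit. The shift differs between visits only as far as growth rate and SD change over the study, so most of it cancels.

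**5. Age bands.** Let a true 17-year-old be aged 17 + a, and let U be the time from 1 January to birth, in years. With birth and screening dates uniform over the year, a and U are independent and uniform on 0 to 1.

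- 1 January: computed age is 17 + a + U. P(a + U ≥ 1) = 0.50 are computed as 18 or older.
- 1 July: computed age is 17 + a + U − 0.5. P(a + U ≥ 1.5) = 0.125 reach 18, and P(a + U < 0.5) = 0.125 fall below 17. In total 25% are misbanded, against 50% now.
- Day missing, first of the month: enumerating dates gives about 4% computed as 18 or older.

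Example: born 15 December 1999 and screened 1 July 2017, a child is 17.54 years old. With 1 January 1999 the computed age is 18.50, which fits no band.

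**The case against.** The strongest reply is that this is a last resort that may never be used. Age is sought in IVRS first. SAP 4.1 also states: "Randomization across dose groups will be stratified by age: <1 year, 1 to <12 years, 12 to <17 years, and 17 to <18 years". The system should therefore already hold at least the band for every randomized child. (The protocol supplied, at Amendment 2, has no stratification; the SAP is written to amendment 4.) Protocol 9.3 does not show that any site records only the year, and a date not recorded at all would not reach this rule. All of that stands, and it keeps the point minor.

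It does not remove the point. Standard-of-care children choose their arm and have no randomization stratum. A band alone cannot supply the age at each visit that the Z-scores need, and the SAP does not say how fine the IVRS age is.

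A reader might infer more than the documents support:

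- **That children's safety is at risk.** Under Protocol 6.1.8 the sponsor calculates the Z-scores from site data. Nutritional support is adjusted on measured growth and clinical status (Protocol 6.1.12 and Appendix 1), not on these Z-scores.
- **That all growth Z-scores are biased low, or that age is always raised.** BMI Z has no fixed direction, and the error can be zero.
- **That the efficacy result is affected.** The primary endpoint divides PN/IV volume by body weight and does not use age. Only the exploratory age subgroups could be touched.

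**Conclusion.** The point holds within limits. When IVRS has no age and only the birth year is known, the SAP's rule overstates age by about 6 months on average and never understates it. Height, weight and head-circumference Z-score levels in growing children are then biased low. For height the bias averages about 0.6 to 1.3 under growth of 6 to 9 cm/year and an SD of 3.5 to 5 cm, more in very fast growth and almost nothing near adult height.

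Eligibility covers "Male and female children and adolescents, through 17 years of age, who meet the following inclusion criteria" (Protocol 4.2), so a computed age of 18 or more is certainly wrong. It would nonetheless occur in about half of year-only 17-year-olds if dates are uniform. The case of a missing day alone is negligible on average.

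The overall effect cannot be sized, because the number of children reaching the fallback is unknown and may be zero. In a descriptive study this is a convention worth improving, not a threat to its conclusions.

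**What to change.** Amend SAP section 11 so that, where IVRS holds no age, the birth date is imputed as the 15th of the month (day missing) or 1 July (day and month missing). Require the imputed date to be no later than screening, to give an age below 18 at screening, and to agree with the randomization age stratum where one exists. If these limits rule out the default date, use the midpoint of the permitted birth dates. The limits are needed: for an infant, 1 July can fall after screening.

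Take the age band from the stratum for randomized children. State in SAP 19.6.1 that the Z-score program uses the same birth date, and flag Z-scores based on an imputed date in the listing.

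The cost is a few sentences and a little programming, with no change to trial conduct. It is not free of error: individual ages can then be understated as well as overstated, by up to about 6 months. For year-only 17-year-olds in standard of care, the age limit removes results of 18 or more, but the 12.5% computed as under 17 would remain, since they have no stratum to correct them.
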